**Figure 2 Data Collection Periods and Timepoints for Each Patient**

FU = follow-up.

PFIZER CONFIDENTIAL

CT24-WI-GL03-RF03 1.0 *Non-Interventional Statistical Analysis Plan For Secondary Data Collection*  
*Study 16-Sep-2020*  
 Page 10 of 19

## 5 OUTCOME DEFINITIONS

Outcomes will be defined as presented in Table 1.

**Table 1      Outcome Definitions**

Variable	Definition	Timepoint
Death	Death as indicated on the medical record abstraction form.	Post-index period
Clinical response	
Clinical success: Resolution or partial resolution of all attributable clinical symptoms and physical findings.
 
Clinical failure: No resolution of any attributable clinical symptoms and physical findings and/or worsening.
 
When medical record documentation is not clear to the abstractor as to which category should be specified, the investigator should review all available medical record documentation to determine classifications. If the investigator determines there is not enough medical record documentation to make the classification, he or she will indicate that the response is 'unknown'. Since clinical response classification is important to the study, participating sites will be selected for participation in the study based on their reporting whether they have enough medical record documentation to classify the response.
	Post-index period
Radiological response	
Radiological success: <math>\geq 50\%</math> improvement from initial assessment or improvement of at least 25% from the initial assessment for the follow-up at 6 weeks (i.e., day 42 [<math>\pm 14</math> days]) or if end of treatment occurred before this time.
 
Radiological failure: Failure to meet success criteria.
	Post-index period

PFIZER CONFIDENTIAL

CT24-WI-GL03-RF03 1.0 *Non-Interventional Statistical Analysis Plan For Secondary Data Collection*  
*Study 16-Sep-2020*  
 Page 11 of 19

Variable	Definition	Timepoint
	When medical record documentation is not clear enough for the abstractor as to which category should be specified, the investigator should review all available medical record documentation to determine classifications. If the investigator determines there is not enough medical record documentation to make the classification, he or she will indicate that the response is 'unknown.' Since radiological response classification is important to the study, participating sites will be selected for participation in the study based on their reporting whether they have enough medical record documentation to classify the response.	
Mycological response	
Mycological success will be defined as eradication or presumed eradication of the original causative organism cultured.
 
Mycological failure will be defined as persistence or presumed persistence.
 
When medical record documentation is not clear to the abstractor as to which category should be specified, the investigator should review all available medical record documentation to determine classifications. If the investigator determines there is not enough medical record documentation to make the classification, he or she will indicate that the response is 'unknown.' Since mycological response classification is important to the study, participating sites will be selected for participation in the study based on their reporting whether they have enough medical record documentation to classify the response.
	Post-index period

PFIZER CONFIDENTIAL

CT24-WI-GL03-RF03 1.0 *Non-Interventional Statistical Analysis Plan For Secondary Data Collection*  
 Study 16-Sep-2020  
 Page 12 of 19

Variable	Definition	Timepoint
Adverse events	Documentation of any adverse event in the medical record or as described by the ICD-9 or ICD-10 systems.	Post-index period
Serious adverse event	Documentation of any serious adverse event in the medical record or as described by the ICD-9 or ICD-10 systems.	Post-index period
Treatment patterns	Documentation of any of the following in the medical record: 
 
• Index treatment modification
 
• Index treatment discontinuation
 
• TDM
 
• Switching to a new antifungal therapy after index treatment discontinuation
 
• Use of subsequent antifungal therapy after end of index treatment
 
• Index treatment administered as part of antifungal combination therapy
 
• Other concomitant treatments not including combination antifungal therapy
 
• Index treatment administered in the outpatient setting following initiation in the inpatient setting
 
	Post-index period
Healthcare resource utilization	Documentation of any inpatient stay (including specialty wards, ICU, ER, general medicine ward, or other) or outpatient visit (not associated with a hospitalization) in the medical record.	Post-index period

ICD-9 = *International Classification of Diseases, Ninth Edition*; ICD-10 = *International Classification of Diseases, Tenth Edition*; ICU = intensive care unit; ER = emergency room; TDM = therapeutic drug monitoring.

PFIZER CONFIDENTIAL

CT24-WI-GL03-RF03 1.0 *Non-Interventional Statistical Analysis Plan For Secondary Data Collection*  
*Study 16-Sep-2020*  
 Page 13 of 19

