9.2.2. Inclusion Criteria

Patients must meet all of the following inclusion criteria to be eligible for inclusion in the study:

1. Patient must be aged ≥ 18 years at the time of isavuconazole initiation.
2. Patient must have a record of a diagnosis of invasive aspergillosis or mucormycosis in their medical record at the time isavuconazole was initiated (regardless of whether this diagnosis is suspected or confirmed).ⁱ
3. Patient must have received at least one dose of isavuconazole during the eligibility period (October 15, 2015, to June 30, 2019).^j

ⁱ Documented cases of invasive aspergillosis or mucormycosis will be included (providing the patient meets all other study inclusion criteria), regardless of whether the diagnosis is classified as being 'suspected' or confirmed via mycological or radiological assessments (this includes EORTC/MSG classification of "proven," "probable," and "possible" invasive fungal disease). All available sources will be used to confirm diagnosis (including any text in the medical records [eg, discharge diagnosis] and ICD-10 codes, if available). The level of documentation in the medical records is expected to vary by HCP and by site and/or country.

^j The eligibility period end date is subject to change based on timing of medical record abstraction and anticipated number of potentially eligible patients during the proposed eligibility timeframe.

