Fungal disease characteristics	
Disease type
 
 • Invasive aspergillosis; • Mucormycosis. 
Date of suspected diagnosis (DD MMM YYYY) Date of confirmed diagnosis (DD MMM YYYY)
 
Note: Documented cases of invasive aspergillosis or mucormycosis will be included (providing the patient meets all other study inclusion criteria), regardless of whether the diagnosis is classified as being “suspected” or confirmed via mycological or radiological assessments (this includes EORTC/MSG classification of “proven,” “probable,” and “possible” invasive fungal disease). All available sources will be used to confirm diagnosis (including any text in the medical records [eg, discharge diagnosis] and ICD-10 codes, if available). The level of documentation in the medical records is expected to vary by HCP and by site/country.
	At index date or closest assessment to index during the pre-index period. If no assessments are available in the pre-index period, then assessments closest to index in the post-index period will be used.
	
Mycological confirmation:
 
 • Yes; • No; • Unknown. 	
	Date of mycological confirmation (DD/MMM/YYYY) (if applicable)	
	Mycological examination type (if applicable):	

Category	Variable	Timepoint
	
 • Blood or tissue culture; • Bronchoalveolar lavage; • Urine sample; • Biopsy specimen; • Other (specify); • Unknown. 	
	
Radiological confirmation:
 
 • Yes; • No; • Unknown. 	
	
Date of radiological confirmation (DD/MMM/YYYY) (if applicable)
	
	
Radiological assessment type (if applicable):
 
 • Chest X-ray; • CT scan; • Ultrasound; • MRI; • Other (specify); • Unknown. 	
	
Radiographic assessment location:
 
 • Brain; • Lungs; • Liver; • Kidney; • Stomach; • Intestines; • Other (specify); • Unknown. 	
	
Other confirmation type:
 
 • Yes (specify); • No; • Unknown. 	
	
EORTC/MSG disease classification (if available):
 
 • Proven; • Probable; • Possible; • Unknown. 	
	
Localization (all that apply):
 
 • Lungs; • Sinus; 	

Category	Variable	Timepoint

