### 1.3 MUCORMYCOSIS

The main risk factors for mucormycosis include diabetes mellitus, hematological malignancies, stem cell/organ transplantations, corticosteroid therapy, and neutropenia. Mucormycosis usually is diagnosed through identification of causative agents by histopathological analysis of tissue specimens in patients showing symptoms of the infection. However, diagnosis is challenging, and cultures are only occasionally positive. Initial treatment of mucormycosis typically includes surgery to remove infected tissues and antifungal treatment with amphotericin B.

The VITAL clinical trial (NCT00634049) was a single-arm, open-label trial that included an assessment of the efficacy and safety of isavuconazole for treatment of mucormycosis in 37 patients. The primary outcome was independent data review committee-determined overall response (complete or partial response [treatment success] or stable or progressive disease [treatment failure]) at day 42, day 84, and end of treatment. The results demonstrated that by day 42, 11% of patients had a partial response, 43% had stable disease, 3% had disease progression, 8% had missing assessments, and 35% had died. The efficacy of isavuconazole and amphotericin B also was compared in a matched case-control analysis. At day 42, all-cause mortality was similar in cases with isavuconazole as the primary treatment and amphotericin B-treated matched controls (weighted all-cause mortality: 33% vs. 41%;  $P = 0.595$ ).

Although the use of some antifungals are restricted in patients with renal impairment, in a pooled analysis of the SECURE and VITAL trials, isavuconazole was reported to be well tolerated in patients with renal impairment.

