### 3 ANALYSIS POPULATION

The analysis population will consist of adult patients who received isavuconazole for the treatment of invasive aspergillosis or mucormycosis in the hospital setting. Patients who did not receive at least one dose of isavuconazole for treatment of invasive aspergillosis or mucormycosis within the eligibility period will not be considered for analysis.

*Patients must meet all of the following criteria to be eligible for inclusion in the analysis:*

1. *Patient must be aged  $\geq 18$  years at the time of isavuconazole initiation*
2. *Patient must have a record of a diagnosis of invasive aspergillosis or mucormycosis in their medical record at the time isavuconazole was initiated (regardless of whether this diagnosis is suspected or confirmed)*
3. *Patient must have received at least one dose of isavuconazole during the eligibility period (October 15, 2015, to June 30, 2019)*

*All analyses will be performed on the analysis population. Analyses of the primary endpoints may also be performed on up to three subgroups, which will be selected from the following list and determined based on sample size:*

- Neutropenia and non-neutropenia patients
- Patients with central nervous system infections
- Age (e.g.,  $<75$  years vs.  $\geq 75$  years)
- Patients with corticosteroid use at baseline
- Patients with influenza at baseline
- Patients with ICU admission where isavuconazole is initiated
- Patients with history of use of biologics

PFIZER CONFIDENTIAL

[figure not shown]
CT24-WI-GL03-RF03 1.0 *Non-Interventional Statistical Analysis Plan For Secondary Data Collection*  
*Study 16-Sep-2020*  
*Page 8 of 19*

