CT24-WI-GL03-RF03 1.0 *Non-Interventional Statistical Analysis Plan For Secondary Data Collection*  
Study 16-Sep-2020  
Page 15 of 19

For the mycological response outcome, patients will be categorized having the infection eradicated, presumed eradicated, not eradicated (failure), unknown response, or not applicable (for the initial assessment) at relevant timepoints of interest. Additionally, mycological examination type and biomarker categories will be tabulated at post-baseline visits (Appendix 1, Analysis Table 8.1). For KM analyses, mycological response (eradication or presumed eradication) will comprise the event, and patients will be censored at the earliest timepoint of any of the following: loss to follow-up, end of study, or death (Appendix 1, Analysis Figure 4; Appendix 1, Analysis Table 8.2)

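### The mycological Kaplan-Meier keeps patients with no identified organism at risk for an eradication event that, as defined, they cannot have, so the time-to-eradication estimate is diluted

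*SAP*

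**What the plan says.** SAP Table 1 states that mycological success "will be defined as eradication or presumed eradication of the original causative organism cultured"; failure is persistence or presumed persistence. The footnote on mycological response in Protocol 9.4.3 ties the outcome to a cultured organism in the same way. If the record does not support a classification, the investigator enters *unknown*.

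On who is analysed, SAP 3 says "All analyses will be performed on the analysis population", and admits patients with a recorded diagnosis "regardless of whether this diagnosis is suspected or confirmed". Protocol 9.2.2 is more explicit. Cases enter "regardless of whether the diagnosis is classified as being 'suspected' or confirmed via mycological or radiological assessments", and the EORTC/MSG class *possible* is included.

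On the analysis, SAP 6.3 anchors time to event on the index date and covers aspergillosis, mucormycosis and all patients. It then says: "For KM analyses, mycological response (eradication or presumed eradication) will comprise the event". Censoring is at the earliest of loss to follow-up, end of study or death. The tabulated categories are eradicated, presumed eradicated, failure, unknown, and not applicable, the last reserved for the initial assessment. SAP 6.1 bases categorical frequencies on nonmissing observations and allows no imputation.

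At baseline, Protocol 9.4.1 collects "Mycological confirmation" (yes, no, unknown), its date and the examination type.

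**The concern.** The outcome presupposes an organism and the population does not. A patient treated on a suspected or radiological diagnosis has nothing whose eradication could be observed or presumed. The plan still puts that patient at risk from index and keeps the patient there until censoring. Neither document's text defines a mycologically evaluable set, and no analysis category describes a patient who never had an isolate.

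The number affected may be large in one stratum. SAP 1.3 says of mucormycosis that "cultures are only occasionally positive".

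Overall response is a primary outcome, and the protocol abstract lists mycological response among its three parts. A reader of the KM curve would take a low plateau, or a median that is not reached, as slow or poor eradication. It could simply show how often an organism was found. The same problem would enter the optional subgroup log-rank tests and Cox hazard ratios if organism yield differs between subgroups.

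**Working it through.** The documents give no expected mycological response rate, no share of patients with an organism and no precision for this outcome, so there is no plan figure to reproduce. The precision figures in Protocol 9.5 concern mortality only.

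**Step 1: the risk set.** The event needs a cultured organism (SAP Table 1), entry does not (SAP 3, Protocol 9.2.2), the KM starts at index in everyone, and no censoring rule removes patients without an organism (SAP 6.3). The risk set therefore contains patients with zero event probability as the event is written.

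**Step 2: effect on the KM.** Let c be the share of patients with a qualifying organism and F(t) the true eradication probability among them. If both groups have the same follow-up, the curve for all patients is S(t) = (1 − c) + c[1 − F(t)], so 1 − S(t) = c × F(t).

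Assumptions, none from the documents: F = 70% at week 12, a constant hazard λ = −ln(0.30)/84 = 0.01433 per day, and c from 20% to 70%. The median solves c[1 − exp(−λt)] = 0.5 and does not exist for c of 50% or less.

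| c | Week 6 | Week 12 | Week 24 | Median (days) |
|---|---|---|---|---|
| 100% | 45.2% | 70.0% | 91.0% | 48 |
| 70% | 31.7% | 49.0% | 63.7% | 87 |
| 50% | 22.6% | 35.0% | 45.5% | not reached |
| 30% | 13.6% | 21.0% | 27.3% | not reached |
| 20% | 9.0% | 14.0% | 18.2% | not reached |

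If the true week-12 value were 50%, the all-patient figure would run from 0.20 × 50% = 10% to 0.70 × 50% = 35%. If it were 90%, it would run from 18% to 63%.

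**Step 3: the opposing effect of censoring at death.** Use the 19% day-42 mortality quoted for isavuconazole in Protocol 7.2. The death hazard is d = −ln(0.81)/42 = 0.00502 per day. Among patients with an organism, cumulative incidence of eradication at week 12 is λ/(λ + d) × [1 − exp(−84(λ + d))] = 0.7407 × 0.8032 = 59.5%, against 70% from 1 − KM. The two effects cancel where 0.70c = 0.595, that is c = 85%. Over the assumed range of c, dilution dominates.

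**Step 4: the week 6, 12 and 24 percentages.** Suppose patients without an organism are recorded as *unknown*. If *unknown* stays in the denominator, the percentage is again c × F. If it is treated as missing under SAP 6.1, the percentage is F and there is no dilution. The SAP does not say which applies.

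**Step 5: subgroups.** Take two subgroups with identical eradication but c = 20% and c = 50%. Their hazard ratio is 0.20/0.50 = 0.40 at index and moves toward (0.20/0.80)/(0.50/0.50) = 0.25. All of that comes from organism yield.

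**The case against.** The strongest reply concerns the tabulated rate. A reader might infer that the eradication percentage at each timepoint is diluted as well. The documents do not establish this: frequencies use nonmissing observations, *unknown* is shown apart from failure, and response is recorded per dated examination, so a patient never examined may contribute nothing. The table shells sit in an embedded file that is not part of the readable text and could settle the denominator. This stands. For the percentages, the defect in the SAP text is an unstated denominator.

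A reader might also infer that such patients will never be counted as events and that the bias must be downward. That holds for the definition but not necessarily for the data. The case report form accepts presumed eradication for any examination type, and an entry that contradicts the definition would add events. Censoring at death also raises 1 − KM. Neither point justifies the risk set, but the net direction in the final data is not certain.

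Other stronger readings fail. The SAP derives no composite response, so mortality and clinical response are not affected. Its subgroup list contains neither country nor site, although Protocol 9.9 mentions country as a possible subgroup. The two diseases are presented separately without a specified test, and the remark about cultures concerns mucormycosis only.

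Protocol 9.11 does warn that mycological response may be poorly documented. That covers missing records, not patients for whom the outcome is undefined.

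**Conclusion.** The concern holds for the Kaplan-Meier analysis. Followed as written, the plan includes patients who cannot have the defined event and lowers the estimated response probability roughly in proportion to their share. The proportionality assumes similar follow-up with and without an organism, and coding that respects the definition.

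The size cannot be fixed from the documents. The range of 14% to 49% in place of 70% at week 12 is an illustration that rests on an assumed eradication rate and an assumed organism share of 20% to 70%. A median that is never reached follows only if that share is 50% or less.

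For the week 6, 12 and 24 percentages, the conclusion is limited to an unspecified denominator. This is more than missing detail, because a specific restriction using collected fields would change the reported estimate.

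**What to change.** - In SAP 6.3, define a mycologically evaluable set: baseline mycological confirmation recorded as yes, dated on or before index or within a short fixed window after it.
- Reword SAP Table 1 so that identification by histopathology or another non-culture method qualifies. A culture-only rule would not work as the main definition. Protocol 9.4.1 records specimen or examination type but no culture result, and Protocol 7.3 describes mucormycosis as usually diagnosed by histopathology. Add a culture-only sensitivity analysis where the examination type allows it.
- Use the set as the KM risk set (Analysis Figure 4, Table 8.2) and as the denominator of Table 8.1.
- Exclude *unknown* from the percentage denominator and show its count.
- Report patients with no baseline organism on a separate not-evaluable line, and do not accept presumed eradication for them.

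The cost is SAP wording, one derived flag and a data check. The footnote in Protocol 9.4.3 should be aligned. Protocol 9.9 requires an amendment for major changes to primary outcome definitions or analyses, so the sponsor should decide whether this is one.

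The statistical cost is precision. With 600 patients and c of 20% to 70%, the set has 600 × 0.20 = 120 to 600 × 0.70 = 420 patients. The Wilson 95% half-width around 70% is then about 8.1 to 4.4 points. Intervals for mucormycosis would be wider still.

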## 6 STATISTICAL METHODS AND ANALYSIS

### 6.1 STATISTICAL CONVENTIONS

Categorical variables will be reported as counts and frequencies of nonmissing observations. Continuous variables will be reported using the number of nonmissing observations, mean, standard deviation, median, first quartile, third quartile, minimum value, and maximum value. Time-to-event outcomes will be assessed using the Kaplan-Meier (KM) method and will be reported as descriptive statistics with 95% CIs. Results will be presented for the overall group (both disease types) and separately for invasive aspergillosis and mucormycosis. Additionally, subgroup analyses may be performed. If so, log-rank tests will be reported, and Cox regression will be employed with presentation of hazard ratios (HRs) and 95% CIs.

Unless otherwise specified, the time between two dates of interest (including time-to-event analyses) will be computed as the difference between the two calendar dates (e.g., date 2 – date 1) and expressed in days.

No imputation for missing values will be performed. Criteria for censoring in KM analyses will be described for each time-to-event outcome analyzed.

Example tables and figure descriptions for analyses described in this section (analysis tables and analysis figures) are provided in Appendix 1.

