7.3. Mucormycosis

The main risk factors for mucormycosis include diabetes mellitus, hematological malignancies, stem cell/organ transplantations, corticosteroid therapy, and neutropenia.² Mucormycosis is usually diagnosed through identification of causative agents by histopathological analysis of tissue specimens, in patients showing symptoms of the infection.¹ However, diagnosis is challenging, and cultures are only occasionally positive. Initial treatment of mucormycosis typically includes surgery to remove infected tissues and antifungal treatment with amphotericin B.¹

The VITAL clinical trial (NCT00634049) was a single-arm, open-label trial, that included an assessment of the efficacy and safety of isavuconazole for treatment of mucormycosis in 37 patients. The primary outcome was independent data review committee-determined overall response (complete or partial response [treatment success] or stable or progressive disease [treatment failure]) at day 42, day 84, and end of treatment. The results demonstrated that by day 42, 11% of patients had a partial response, 43% had stable disease, 3% had disease progression, 8% had missing assessments, and 35% had died.⁷ The efficacy of isavuconazole and amphotericin B was also compared in a matched case-control analysis.⁷ At day 42, all-cause mortality was similar in cases with isavuconazole as the primary treatment and amphotericin B-treated matched controls (weighted all-cause mortality: 33% vs. 41%; $P = 0.595$).⁷

Although the use of some antifungals are restricted in patients with renal impairment, in a pooled analysis of the SECURE and VITAL trials, isavuconazole was reported to be well tolerated in patients with renal impairment.⁸

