9.9.1. Missing Data

It is anticipated that the degree of completeness for the study variables may vary due to unknown or undocumented data in the medical records. The number of patients with missing data for each variable will be summarized and reported. With the exception of the imputation of partial missing date values, no other imputation of missing values is anticipated; however, the impact of missing data on interpretation of findings will be acknowledged and discussed in the final study report. The SAP will further provide a detailed description of methods to deal with missing data and censoring.

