### 6.3 ANALYSIS OF CLINICAL OUTCOMES

Each clinical outcome will be analyzed using counts and frequencies at weeks 6, 12, and 24, along with other descriptive information about the clinical outcome itself.

Additionally, time-to-event analyses anchored on the index date of isavuconazole initiation will be performed using the KM method. For each clinical outcome, the time-to-event analyses will result in a KM plot with summary statistics, including survival-time quartiles and KM estimates at weeks 6, 12, and 24 with accompanying 95% CIs. All analyses will be performed for invasive aspergillosis patients, mucormycosis patients, and for the total study population. If subgroup analyses are pursued, Cox regression will be employed to derive HRs and accompanying 95% CIs.

For the death outcome, patients will be categorized as dead, alive, or unknown at each timepoint of interest, and primary cause of death will be tabulated (Appendix 1, Analysis Table 5.1). For KM analyses, a documented death will comprise the event, and patients will be censored at the date when they are last known to be alive (Appendix 1, Analysis Figure 1; Appendix 1, Analysis Table 5.2).

For the clinical response outcome, patients will be categorized as having clinical success, having clinical failure, or unknown response at each timepoint of interest will be tabulated (Appendix 1, Analysis Table 6.1). In addition, rates of reactivation of the same infection and rates of new infection will be documented overall and specific to whether these events occurred during isavuconazole treatment. For KM analyses, clinical response will comprise the event, and patients will be censored at the earliest timepoint of any of the following: loss to follow-up, end of study, or death (Appendix 1, Analysis Figure 2; Appendix 1, Analysis Table 6.2).

For radiological response, patients will be categorized as having a success, not having a response, unknown response, or not applicable (for the first assessment) at the relevant timepoints of interest (Appendix 1, Analysis Table 7.1). Additionally, radiological examination type and bodily location of the examination will be tabulated. For KM analyses, radiological response will comprise the event, and patients will be censored at the earliest timepoint of any of the following: loss to follow-up, end of study, or death (Appendix 1, Analysis Figure 3; Appendix 1, Analysis Table 7.2).

PFIZER CONFIDENTIAL

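### SAP 6.3 has no place for patients who died before week 6, 12 or 24 in the response tables, and the nonmissing rule in SAP 6.1 can turn those rates into survivor-only rates

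*SAP*

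**What the plan says.** Two general rules stand in SAP 6.1: "Categorical variables will be reported as counts and frequencies of nonmissing observations" and "No imputation for missing values will be performed".

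SAP 6.3 gives the categories used at weeks 6, 12 and 24.

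- Clinical response (Table 6.1): "patients will be categorized as having clinical success, having clinical failure, or unknown response at each timepoint of interest".
- Radiological response (Table 7.1): success, no response, unknown, and a not-applicable category for the first assessment.
- Mycological response (Table 8.1): eradicated, presumed eradicated, failure, unknown, and again not applicable for the initial assessment.
- Death (Table 5.1): "patients will be categorized as dead, alive, or unknown at each timepoint of interest".

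Only the mortality table has a category for the dead. SAP Table 1 ties an unknown response to the investigator's finding that the chart holds too little to decide; it does not mention death. The Kaplan-Meier analyses of time to response in SAP 6.3 censor at death.

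On missing data, Protocol 9.9.1 promises: "The number of patients with missing data for each variable will be summarized and reported". Protocol 7.3 describes the day-42 results of VITAL with the dead as a group of their own: "8% had missing assessments, and 35% had died".

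**The concern.** Overall response is named with all-cause mortality in the first primary objective. SAP Table 1 defines only its three components, so Tables 6.1, 7.1 and 8.1 carry what the SAP reports on response.

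A patient who dies in week 3 has no week-12 assessment. If that is treated as a missing observation, the rule in SAP 6.1 removes the patient from the percentage. The table then answers a different question (response among patients alive and assessed), while a reader is likely to take it as the response rate of treated patients. A comparison with VITAL would also rest on different denominators. If the patient is entered as 'unknown' instead, a known death is merged with an undocumented outcome.

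The Kaplan-Meier analyses do not settle the matter. They censor at death and so do not count it as a failure to respond either. This point concerns the cross-sectional tables only.

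**Working it through.** **Inputs**

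- Day-42 mortality in invasive aspergillosis, 19% (SECURE; Protocol 7.2 and Table 1).
- Day-42 outcomes in mucormycosis, n = 37 (VITAL; Protocol 7.3): partial response 11%, stable 43%, progression 3%, missing 8%, died 35%.
- The documents give no expected response rate and no week-12 or week-24 mortality. Response rates of 30% to 60% below are assumptions.

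**The plan's own figures**

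Protocol Table 1 uses the 19%. The Wilson width is 2z·√(p(1−p)/n + z²/4n²) / (1 + z²/n), with p = 0.19. For N = 292, 237, 152 and 106 it gives 8.98, 9.96, 12.41 and 14.83 points, against 9.0, 10.0, 12.5 and 15.0 in the table. The table reproduces.

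The VITAL percentages correspond to counts of 4, 16, 1, 3 and 13. These sum to 37 and give 10.8%, 43.2%, 2.7%, 8.1% and 35.1%. The quoted percentages sum to 11 + 43 + 3 + 8 + 35 = 100, so the dead and the missing are both in VITAL's denominator.

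**VITAL pattern under each reading**

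| Denominator | Response |
|---|---|
| All treated | 4/37 = 10.8% |
| Dead dropped | 4/(37 − 13) = 4/24 = 16.7% |
| Dead and missing dropped | 4/(37 − 13 − 3) = 4/21 = 19.0% |
| Dead coded 'unknown' and kept | 4/37 = 10.8% |

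**General form**

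Let R be responders divided by all patients at index, d the share dead by the timepoint, and q the share of the dead who leave the denominator. The dead who stay count as non-success. The tabulated rate is then R/(1 − qd), so the factor is 1/(1 − qd).

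| q | d = 19% | d = 35% |
|---|---|---|
| 0 | 1.00 | 1.00 |
| 0.5 | 1/0.905 = 1.10 | 1/0.825 = 1.21 |
| 1 | 1/0.81 = 1.23 | 1/0.65 = 1.54 |

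With d = 19% and q = 1, assumed response rates of 30%, 40%, 50% and 60% would be tabulated as 37.0%, 49.4%, 61.7% and 74.1%, a gain of 7 to 14 points.

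**The case against.** The strongest reply is that the SAP nowhere says the dead are excluded.

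- SAP 6.3 categorizes patients, not assessments, and 'unknown' is a recorded value. A dead patient coded 'unknown' is arguably nonmissing and stays in the denominator, which gives a factor of 1.00. This stands. It removes the inflation, but deaths still sit with poor charting, and the SAP does not say whether 'unknown' counts as nonmissing.
- SAP Table 1 defines radiological failure as anything short of success, so a patient who died without success could be counted there. This is a possible reading for Table 7.1. The clinical and mycological definitions have no such catch-all.
- Some patients will have been rated before death. The week-6 radiological window is day 42 ± 14 days, so a death on day 35 may follow a valid assessment. This stands, and it is why the factors for q = 1 are upper limits.
- The layouts of Tables 6.1, 7.1 and 8.1 are in an attached file (SAP Appendix 1) whose content is not in the text. They may settle the denominator.
- Deaths are tabulated separately at the same timepoints, and Protocol 9.9.1 requires missing counts. A reader could see a shrunken denominator, but missing counts alone would not separate deaths from undocumented cases.
- Counting every death as a treatment failure would impose a composite outcome, and a documented responder may later die of the underlying disease. This is a fair point. A separate row for death avoids that label.

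A reader might infer that the dead do drop out and that the reported rates will be inflated. The documents do not support that as a fact: it is the natural reading of SAP 6.1 with 6.3, not the only one. A reader might also infer that response will seem to rise from week 6 to week 24 as non-responders die. That could happen under exclusion, but no later mortality is given from which to judge it.

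**Conclusion.** The point holds as a gap in the rules for the component response tables. The SAP text does not say where a patient who died before the timepoint is counted, and its one stated rule on denominators permits exclusion. Each reading has a cost: survivor-only rates if the dead are left out, or deaths merged with undocumented outcomes if they are coded 'unknown'.

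The effect of deaths alone lies between no inflation and a factor of 1.23 at 19% mortality, or 1.54 at 35%. The upper ends assume that every patient dead by the timepoint leaves the denominator and that none of them counts as a success. Dropping missing assessments as well adds to this, as the 19.0% on the VITAL pattern shows. The VITAL counts are inferred from rounded percentages of 37.

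This is an inexpensive improvement to a result that bears on a primary objective, not proof that the planned rates are wrong.

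**What to change.** In SAP 6.3, for Tables 6.1, 7.1 and 8.1:

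- Add a separate row, 'died before the timepoint'.
- Use as denominator all patients eligible for that outcome at index, and state for each outcome who they are.
- Show 'unknown' and missing as separate rows within that denominator.
- Give the rate among assessed survivors only as a labelled secondary figure.

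In SAP 6.1, state that the nonmissing rule does not apply to these response tables. If the Appendix 1 shells already have such a row and denominator, the text of 6.1 and 6.3 need only be brought into line with them.

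The cost is a few sentences and, where the shells lack them, extra rows in three tables. No new data are needed, since dates of death and of assessments are already collected. Protocol 9.9 provides for a revised SAP before data collection is complete. The downside is that reported success rates become lower than under a nonmissing denominator, and a responder who dies before a later timepoint moves to the death row there.
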